#### 4.2.4 Blinding plan – unblinding plan

When assigning the CSS, the evaluators will be blind to the image time point and therefore, will not know whether the image is prior to or post-procedure. The evaluators will not know which image is baseline or follow-up and will be asked to identify the baseline.

Once the CSS and baseline image estimates are completed, the image pairs will then be presented with the baseline and follow-up known for the GAIS in the unblinded assessment.

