### 4.2.2 Frequency and Order of Evaluations

The evaluations will occur in advance of each planned interim analysis as outlined in **Table 3** and will follow the order outlined to ensure no pre-mature unblinding of the before/after that is required for the GAIS evaluation.

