**Table 3 Independent Image Evaluation Scope**

Evaluation session number	Assessment type	Visit Time Points	Blinded
#1, at 3-month analysis	CSS ID of BL	Baseline and 30-day Baseline and 3-month	Yes, time point redacted
#1, at 3-month analysis, after CSS	GAIS	Baseline and 30-day Baseline and 3-month	No, improvement intentionally assessed
#2, at 6-month analysis	CSS ID of BL	Baseline and 6-month	Yes, time point redacted
#2, at 6-month analysis, after CSS	GAIS	Baseline and 6-month	No, improvement intentionally assessed
#3, at 12-month analysis	CSS ID of BL	Baseline and 12-month	Yes, time point redacted
#3, at 12-month analysis, after CSS	GAIS	Baseline and 12-month	No, improvement intentionally assessed

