### 6.3.6 COVID-19 Contingency

As outlined in section Error! Reference source not found., before blinded photometric evaluation of CSS, the number of participants with images available for the 3-month endpoint will be confirmed. If the number of participants with images cannot adequately power the endpoint (N=54) due to excessive 3-month COVID 19 related missed visits, the primary endpoint time point will be changed to 6-month. Of note, the inferential secondary endpoints will similarly change to 6-month (section 6.5).

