#### Hypothesis:

- $H_0: D < 1$
- $H_a: D \geq 1,$

where  $D$  = improvement in the CSS score from baseline to 3 months, and 1 is the performance goal.

The endpoint with a sample size of 54 participants will be adequately powered with at least 90% power to test the hypothesis that the mean reduction at 3-months is equal to or greater than 1. This study's sample size will be increased by 25% for a total N of 68 to account for the potential of missed visits amid the pandemic.

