##### 6.5.1 Hierarchical testing

If the primary endpoint passes, a subset of the secondary endpoints (inferential) will have hypothesis tests performed for potential labeling claims. These endpoints will be tested the specific order presented below. If the first secondary endpoints passes the hypothesis test (rejects the null hypothesis), then the next secondary endpoint will be tested. Testing will continue up to the point that a hypothesis test fails. Endpoints that follow will then simply use descriptive statistics and no p-values will be presented. Since this testing relies first on the primary endpoint

passing, the 6-month data will be used instead should 3-month COVID 19 related missed visits reduce the evaluable data to <54.

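### If the COVID-19 contingency moves the primary endpoint to 6 months, no text holds back session-1 GAIS, so the new primary CSS could be read after evaluators had seen labelled baselines

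*Combined protocol and SAP*

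**What the plan says.** **Reading order.** Table 3 sets three evaluation sessions. Session 1 covers baseline/30-day and baseline/3-month pairs, session 2 baseline/6-month pairs, and session 3 baseline/12-month pairs. In each session the CSS and the identification of baseline come first, marked "Yes, time point redacted", and GAIS follows without blinding. Section 4.2.4 says that after the CSS is done "the image pairs will then be presented with the baseline and follow-up known for the GAIS in the unblinded assessment". Section 4.2.2 states the purpose: the evaluations "will follow the order outlined to ensure no pre-mature unblinding of the before/after that is required for the GAIS evaluation".

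**Contingency.** Section 6.3.6 says that "before blinded photometric evaluation of CSS, the number of participants with images available for the 3-month endpoint will be confirmed". If COVID-19 related missed visits leave too few for the required 54, "the primary endpoint time point will be changed to 6-month", and "the inferential secondary endpoints will similarly change to 6-month". Section 6.5.1 repeats the rule for the gatekept tests: "the 6-month data will be used instead should 3-month COVID 19 related missed visits reduce the evaluable data to <54".

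**Readers and masking.** Section 4.2.1 describes one panel of three physicians. Section 4.2.3 hides the participant ID, recodes the photo ID and randomises which set appears at the top of the screen.

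**Size.** In section 6.3.7 the "sample size will be increased by 25% for a total N of 68", starting from 54.

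**The concern.** This is a single-arm, open-label trial whose primary endpoint is scored from photographs. With no control group, the main protection against reader expectation in the change score is that the evaluator does not know which image set is the baseline. The plan recognises this and orders CSS before GAIS.

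That order protects the planned 3-month primary, because its CSS is read before any GAIS. It does not carry over to a primary moved to 6 months. By then the panel could already have been shown the same participants' baseline sets labelled as baseline. Table 1 schedules pre-treatment study photography on Day 0 only, so the same baseline session is the natural comparator each time. The 6-month CSS would still be called blinded, with a weaker blind behind it. Two tests would be exposed: the primary, and the first gatekept secondary (CSS responders, section 6.5.2).

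**Working it through.** **1. The passages set side by side**

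| Step | Source | What it fixes | What it leaves open |
|---|---|---|---|
| CSS before GAIS | 4.2.4, Table 3 | Order within a session | Whether GAIS waits for a later session's CSS |
| Session 1 before session 2 | Table 3 | 30-day and 3-month GAIS precede 6-month CSS | Any change if the contingency is used |
| Image count before CSS | 6.3.6 | The trigger is known before any session-1 read | What then happens to session 1 |
| Move to 6 months | 6.3.6, 6.5.1 | New time point for the primary and inferential secondaries | Reading order, panel, washout |
| Masking | 4.2.3 | Hides ID and label | Does not alter image content, so recognition remains possible |

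No row holds session-1 GAIS, and no supplied section does so elsewhere.

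**2. The plan's own figure**

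54 × 1.25 = 67.5, rounded up to 68. This agrees with section 6.3.7 and with the synopsis (74 enrolled − 6 roll-in = 68).

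**3. How many baselines could have been shown labelled (mITT only)**

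- The trigger requires fewer than 54 with 3-month images, so at most 53 participants could have a labelled 3-month pair: 53/68 = 78%.
- At least 68 − 53 = 15 (22%) would have none.
- Session 1 also includes baseline/30-day pairs, so up to all 68 baselines could have been shown labelled.
- If exactly 53 had 3-month images and all were shown, then of any 54 participants read at 6 months at least 54 − 15 = 39 would already have appeared in a labelled 3-month pair.

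These counts leave out the six roll-in participants, whose images may also be read (sections 6.1.1 and 6.6.1).

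**4. What a hold would cost in time**

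Table 1 defines a month as 30 days and allows +4 weeks at both visits.

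- 3-month window closes: 90 + 28 = day 118.
- 6-month window closes: 180 + 28 = day 208.
- Difference: 208 − 118 = 90 days.

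This is the gap between window closings. The dates of the reading sessions are not given.

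**5. What cannot be computed**

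The documents give no rate of image recognition and no estimate of how a known baseline would shift a CSS score. The size of any bias, and its effect on the error rate, cannot be derived.

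**The case against.** The strongest reply is that this is an unstated step, not a planned unblinding. The document is an abbreviated protocol. The cross-reference that opens section 6.3.6 is broken, and the section it should point to is a natural place for a hold. Section 4.2.2 states the aim of avoiding early unblinding, and the image count comes before the CSS read, so the sponsor could defer session 1 in time. This stands as a limit: a hold may exist elsewhere, and if so it need only be cited. It does not close the gap in the text, because section 4.2.2 pursues its aim only by following Table 3, and Table 3 itself puts session-1 GAIS ahead of session-2 CSS.

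The second reply is that harm needs a chain of events. COVID-19 missed visits must remove at least 15 of 68 participants' 3-month images despite the 25% inflation, session 1 must still run, the same evaluators must return, and they must recognise images months later under new IDs. This also stands. It limits the weight of the point, but the contingency was written for just such a shortfall and the remedy is a change of order.

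A reader might go further and infer three things that the documents do not support:

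- *That the planned 3-month primary is compromised.* It is not. Table 3 and section 4.2.4 already complete session-1 CSS before GAIS.
- *That the plan says session 1 will run in the fallback.* It does not say so. The report schedule in section 6.5 describes the ordinary course, with the primary in the first report, and is silent on the fallback.
- *That the 6-month CSS would be biased by a known amount.* Only exposure can be shown.

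**Conclusion.** The point holds as a gap in the contingency. As written, the order allows a 6-month primary CSS and the CSS-responder test to be read after the panel has seen labelled baselines: up to 68 mITT baselines through 30-day pairs, and at most 53 of 68 (78%) through 3-month pairs. This is possible exposure, not demonstrated unblinding.

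It rests on three assumptions: the COVID-19 trigger is met, session-1 GAIS goes ahead on the Table 3 timetable, and the same three evaluators read both sessions. The last is implied by the single panel in section 4.2.1 but is not stated. In the ordinary course the 6- and 12-month CSS reads also follow a labelled GAIS, but no planned hypothesis test rests on them. The correction is worth making because it is cheap and protects the main safeguard of a single-arm, image-read endpoint. Confidence is medium, given the abbreviated text and the broken reference.

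**What to change.** Add one sentence to section 6.3.6 and to Table 3: *If the primary time point moves to 6 months, no GAIS read takes place until all baseline/6-month CSS and baseline-identification reads are locked.* The rule can be applied in time, because the image count precedes the CSS read and so precedes any GAIS.

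**Cost.** No extra evaluators, visits or images, and no change to the sample size. Only if the contingency is used, the descriptive 30-day and 3-month GAIS results come later, by about 90 days on the visit windows. The inferential GAIS test moves to 6 months in that case anyway.

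**What it does not do.** If session-1 CSS is still read in the fallback, evaluators may recognise images they have seen without labels. The hold removes only the exposure to labelled baselines.

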#### 4.2.5 Cellulite Severity Score (CSS)

Severity scoring by the independent, blinded assessors	
PART A- Number of evident depressions	
0	None
1	Mild ( $\leq 4$ depressions)
2	Moderate (5 to 9 depressions)
3	Severe ( $\geq 10$ depressions)
PART B – Average depth of depressions	
0	None
1	Mild (1-2 mm)
2	Moderate (3-4 mm)
3	Severe ( $\geq 5$ mm)
TOTAL CSS SCORE	= (PART A + PART B) – 1
Note: If both CSS A and CSS B have classifications of 0, the CSS total score will be 0.	

#### 4.2.6 Global Aesthetic Improvement Scale (GAIS) Evaluation

The evaluators will rate the overall improvement on the follow-up image according to the GAIS, per the scale outlined below.

**Table 4 GAIS Categories**

Rating	Assessment	Description
-3	Very much worse	The treated area appearance is obviously worse than before procedure
-2	Much Worse	The treated area appearance is markedly (or significantly) worse than before procedure
-1	Worsened	The treated area appearance is slightly worse than before procedure
0	Unaltered (no change)	The treated area appearance is essentially the same

Rating	Assessment	Description
+1	Improved	Noticeable improvement in appearance of the treated areas, but subtle in magnitude
+2	Much improved	Marked or significant improvement in appearance in the treated areas
+3	Very much improved	Optimal cosmetic result in the treated areas for this subject. No additional treatment is indicated.

## 5 CLINICAL EVENTS

At each evaluation, the investigator will determine whether any adverse events (AEs) have occurred. For the purpose of this protocol, an adverse event is any undesirable medical occurrence in a device user or participant. This definition does not depend on a causal relationship with the device or the protocol requirements. Adverse events reporting will begin at the time the deployable hook procedure is initiated and through participant exit. An adverse event eCRF will be completed for each diagnosed adverse event and followed through resolution or study exit.

### 5.1 ADVERSE EVENT TYPES AND DEFINITIONS

#### 5.1.1 Adverse Event

For the purpose of this protocol, to simplify across USA and Australia, an adverse event will be defined broadly as any undesirable medical occurrence in a device user or participant.

Only procedure-emergent adverse events will be captured. Therefore, all adverse events or pre-existing events that worsen in severity will only be captured after the index procedure.

#### 5.1.2 Serious Adverse Events (SAEs)

An adverse event that led to any of the following:

- a) Death
- b) Serious deterioration in the health of the participant, users, or other persons as defined by one or more of the following:
  - 1) A life-threatening illness or injury, or
  - 2) A permanent impairment of a body structure or a body function including chronic diseases, or
  - 3) In-patient or prolonged hospitalization, or
  - 4) Medical or surgical intervention to prevent life-threatening illness or injury, or permanent impairment to a body structure or a body function,
- c) Fetal distress, fetal death, a congenital abnormality, or birth defect including physical or mental impairment

### 5.1.3 Anticipated Adverse Events

The anticipated risks associated with body contouring procedures in general are listed in **Table 5**. There are no additional unique risks associated with this procedure. The list covers the scope of risks anticipated for device use and procedure. Therefore, these could potentially be associated with anesthesia infiltration, subcutaneous tissue release, liposuction, cellulite reduction procedures and other methods of body contouring in general.

**Table 5 Anticipated Adverse Effects**

Anticipated Adverse Effects List	
Abscess	Inflammation / generalized redness
Anetoderma	Nausea/vomiting
Anxiety (nervousness, apprehension)	Numbness, tingling, or sensitivity change
Blanching (generalized whiteness)	Red Spots (from needle punctures related to anesthesia delivery)
Bleeding	Redness, erythema, or rash
Blurred or double vision	Scarring or keloid formation
Dizziness, drowsiness, confusion, fainting	Sensations of heat or cold
Ecchymosis/bruising	Seroma
Fluid extravasation (leakage of fluid)	Skin necrosis
Hematoma or hard bruise	Skin surface convexity, depression or other irregularity
Hemosiderosis	Soreness or discomfort (pain)
Hyperpigmentation	Swelling/edema
Hypopigmentation	Tinnitus
Induration, fibrosis	Toxic, allergic, or other reaction from the injected anesthetic
Infection	-----

### 5.1.4 Unanticipated Adverse Events

#### 5.1.4.1 Unanticipated Adverse Device Effects (UADEs) For sites in the United States

Any serious adverse effect on health or safety, any life-threatening problem or death caused by, or associated with a device, if that effect, problem, or death was not previously identified in nature, severity, or degree of incidence in the application; or any other unanticipated serious

**Abbreviated CONFIRM Protocol**

problem associated with a device that relates to the rights, safety, or welfare of participants per 21 CFR 812.3.

**5.1.5 Adverse Device Effect (ADE)**

This type of AE is specifically related to the use of an investigational medical device. This definition includes adverse events resulting from insufficient or inadequate instructions for use, deployment, implantation, installation, or operation, or any malfunction. This definition includes any event resulting from use error or from intentional misuse of the investigational medical device.

It is important to point out the difference between a device related AE and an ADE. A device related AE could also qualify as an ADE, with ADE being a subset of device related AEs. For example, mild to moderate bruising is a device related AE, but is a part of a normal recovery course for a cellulite procedure.

**5.2 NOT CONSIDERED ADVERSE EVENT**

- Pre-existing Conditions: Any condition that is recorded in medical records and diagnosed prior to the deployable hook procedure, is considered a pre-existing condition. This condition is not considered an adverse event unless there is a clinically significant worsening of that condition in terms of nature, severity, or degree of incidence.
- Device Deficiencies or Malfunctions: An undesirable technical event during procedure is not an adverse event in itself. However, if a device deficiency or malfunction leads to a medically undesirable situation, then that event must be reported on an Adverse Event Form and is an Adverse Device Effect (ADE).
- Lack of improvement of cellulite is not considered an adverse event.
- Pre-planned hospitalization for any pre-existing condition.
- Any procedure the participant undergoes after the deployable hook is not considered an adverse event, however, the condition leading to the procedure is an adverse event.

**5.3 ADVERSE EVENT ASSESSMENT**

**5.3.1 Adverse Event Evaluation and Categorization**

All AEs will be assessed by the investigator(s). The study will use the Common Terminology Criteria for Adverse Events (CTCAE) Version 5 for AE terminology and severity grading. In addition, the investigator will assess relatedness (device or procedure, none). Guidelines for Investigators follow.

**Table 6 CTCAE Guidance and Database Access**

Search database	https://safetyprofiler-ctep.nci.nih.gov/CTC/CTC.aspx
Printable Quick Reference	https://ctep.cancer.gov/protocolDevelopment/electronic_applications/docs/CTCAE_v5_Quick_Reference_8.5x11.pdf

Clean, Tracked and Mapping Document	Will be provided by Sponsor in study files
-------------------------------------	--

**5.3.2 Severity (Grades)**

**Grade 1** Mild; asymptomatic or mild symptoms; clinical or diagnostic observations only; intervention not indicated.

**Grade 2** Moderate; minimal, local or noninvasive intervention indicated; limiting age-appropriate instrumental activities of daily living (ADL).

**Grade 3** Severe or medically significant but not immediately life-threatening; hospitalization or prolongation of hospitalization indicated; disabling; limiting self-care ADL.

**Grade 4** Life-threatening consequences; urgent intervention indicated.

**Grade 5** Death related to AE.

**Table 7 CTCAE Library Example**

CTCAE TERM	GRADE 1	GRADE 2	GRADE 3	GRADE 4	GRADE 5
Seroma	Asymptomatic; clinical or diagnostic observations only; intervention not indicated	Symptomatic; simple aspiration indicated	Symptomatic, elective invasive intervention indicated	-	-
Bruising	Localized or in a dependent area	Generalized	-	-	-
Pain of skin (characterized by a sensation of marked discomfort in the skin)	Mild pain	Moderate pain; limiting instrumental ADL	Severe pain; limiting self-care ADL	-	-

**5.3.3 Determination of the Relationship (Causality)**

The Investigator, on the basis of his or her clinical judgment, should determine whether there is a reasonable possibility the study device or procedure caused or contributed to the event.

Guidelines to assess AE/SAE/UADE are provided below:

**Not related:** The adverse event is determined to be solely caused by the underlying disease, disorder or condition of the participant, or attributable solely to other extraneous causes (unrelated to the device, device malfunction, or the procedure).

**Abbreviated CONFIRM Protocol**

**Unlikely related:** The adverse event has onset within a clinically relevant temporal relationship to exposure to the device or procedure and is plausibly at least partially caused by or aggravated by the use of the device, device malfunction, or the procedure. It must also meet one of the following criteria: (1) follows a known or easily foreseen pattern of response to device use or procedure and (2) is not fully attributable to the underlying disease, disorder or condition of the participant, or attributable to other extraneous causes.

**Possibly related:** The adverse event has onset within a clinically relevant temporal relationship to exposure to the device or procedure and is more likely than not to be at least partially caused by or aggravated by the use of the device, device malfunction, or the procedure. It must also meet both of the following criteria: (1) follows a known or easily foreseen pattern of response to device use or procedure; and (2) is not fully attributable to the underlying disease, disorder or condition of the participant, or attributable to other extraneous causes. In addition, if the adverse effect is reversible upon reoperation or device exchange, and such a procedure is done, the effect disappears or lessens in severity within the expected time interval.

**Probably/highly probably related:** The adverse event is clearly caused by the use of the device, device malfunction, or the procedure. It must meet all the following criteria: (1) has a clear temporal relationship between device exposure and onset of the event; (2) follows a known pattern of response to device use or procedure; and (3) is not reasonably attributable to the underlying disease, disorder or condition of the participant, or attributable to other extraneous causes. In addition, if the adverse effect is reversible upon reoperation or device exchange, and such a procedure is done, the effect disappears or lessens in severity within the expected time interval.

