## 6.2 SAFETY ANALYSIS

### 6.2.1 Primary Safety Endpoint

Safety will be demonstrated by the absence of device related Serious Adverse Events (SAEs) directly attributable to the device through 30 days post-procedure. All participants that underwent the index procedure will be included in this analysis.

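### Section 5.3.3 defines *Unlikely related* as plausibly caused and holds novel events at that tier, and no supplied section says which rating counts in the zero-SAE safety endpoint

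*Combined protocol and SAP*

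**What the plan says.** Section 5.3.3 opens with a general test: the investigator judges "whether there is a reasonable possibility the study device or procedure caused or contributed to the event". Four tiers follow as guidelines for AEs, SAEs and UADEs.

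- *Not related*: the event is "determined to be solely caused by the underlying disease, disorder or condition of the participant", or is due wholly to other outside causes.
- *Unlikely related*: the timing is relevant and the event "is plausibly at least partially caused by or aggravated by the use of the device, device malfunction, or the procedure". This tier carries a further condition, namely that the event "meet one of the following criteria: (1) follows a known or easily foreseen pattern of response to device use or procedure and (2"), the second criterion being that other causes do not fully explain it.
- *Possibly related*: the timing is relevant and the event "is more likely than not to be at least partially caused by or aggravated by the use of the device". The further condition for this tier is that the event "meet both of the following criteria: (1) follows a known or easily foreseen pattern of response to device use or procedure", together with the same second criterion.
- *Probably/highly probably related*: the event is clearly caused by the device, a malfunction or the procedure. Its criteria include "(2) follows a known pattern of response to device use or procedure".

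Section 6.2.1 defines the primary safety endpoint as the "absence of device related Serious Adverse Events (SAEs) directly attributable to the device through 30 days post-procedure", in everyone who underwent the procedure. The synopsis uses nearly the same words. Section 5.3.1 gives a different relatedness scheme (device or procedure, or none). Section 5.1.5 describes an adverse device effect (ADE) as a subset of device related AEs, and 5.2 makes harm from a malfunction an ADE.

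**The concern.** A causality label should tell the reader how strongly the event is linked to the device. Here an investigator who goes by the label and one who goes by the definition could place the same event in different tiers. A reader who sees *Unlikely related* would take it to mean probably not caused by the device, when the definition says causation is plausible.

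The pattern criteria add a second problem. They make the rating depend on whether the effect was already recognised, not only on whether the device caused it. For an investigational device, unrecognised effects are the ones a safety assessment most needs to rate correctly.

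The stakes come from the endpoint. It is met only if there are no qualifying SAEs, so a single rating can decide it. If the qualifying rating is not fixed beforehand, the choice could be made after an SAE is known.

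**Working it through.** The plan gives no figure on this point, so the check is mainly a comparison of text.

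**1. Labels against definitions.**

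| Label | Causal strength required | Supporting conditions | Does the label fit? |
|---|---|---|---|
| *Not related* | Other causes only | None | Yes |
| *Unlikely related* | Plausible, at least in part | Relevant timing; one of two criteria (pattern; not fully explained otherwise) | No |
| *Possibly related* | More probable than not, at least in part | Relevant timing; both criteria | No |
| *Probably/highly probably related* | Clear | Clear timing; known pattern; no other reasonable explanation | Slightly understated |

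**2. The gap at the bottom.** An event with only a remote chance of relation fails *Not related*, because other causes are not established as the sole cause. It also fails *Unlikely related*, because causation is not plausible. It has no proper tier.

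**3. Against the section's own test.** An event judged plausibly caused appears to meet the reasonable-possibility test, yet it is labelled *Unlikely*.

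**4. The pattern rule.** Take an event with a clear temporal link, clearly caused by the device and with no other explanation.

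- Pattern known: it qualifies for *Probably/highly probably*.
- Pattern foreseeable but not known: it fails the top tier and can reach only *Possibly*.
- Neither: it fails both upper tiers. If the *Unlikely* list means either criterion, it meets the second and is rated *Unlikely*. If the list is read as requiring both, it fits no tier.

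The *Unlikely* list asks for one criterion but joins the two with *and*. The natural reading is *or*.

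**5. What the endpoint phrase could refer to.**

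- The tiers: 6.2.1 names none, and each related tier pools device, malfunction and procedure, so a tier alone does not show device attribution.
- The 5.3.1 categories: these may supply a related/not-related split, but 6.2.1 does not refer to them, and 5.3.1 does not say how device and procedure are told apart.
- The ADE definition in 5.1.5 and 5.2: this is the closest text on device attribution, but it gives no tier and is not linked to the endpoint.

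**6. Effect of one rating.** The synopsis plans 74 participants, including 6 roll-ins; I assume all are treated. The limits are exact (Clopper-Pearson), two-sided 95%.

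- 0/74: upper limit = 1 − 0.025^(1/74) = 4.9%.
- 1/74 = 1.4%: lower limit = 2.5% quantile of Beta(1, 74) = 0.03%; upper limit = 97.5% quantile of Beta(2, 73) = 7.3%.
- With 68 treated (74 − 6): 0/68 gives 0 to 5.3%; 1/68 = 1.5% gives 0.04 to 7.9%.

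The estimate and interval move modestly, but the endpoint goes from met to not met. Section 6.2.1 sets no rate or interval as a criterion, so these limits only show scale. The documents give no SAE rate, so I put no probability on the event.

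**The case against.** The strongest reply is that the tiers are only guidelines under a sensible general test, and that safety information does not disappear. Section 6.2.2 provides SAE narratives and a separate summary of unanticipated events, 5.4 requires evaluation and reporting of UADEs, and 5.6 has an independent Medical Monitor review all AEs. UADE status does not depend on a tier. All of this stands and limits the consequence, but it neither corrects the labels nor says what counts in 6.2.1.

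It can also be said that 5.3.1 already supplies a related yes/no and points on to the guidance in 5.3.3. That is a fair reading for the related Grade 3 and higher AEs in 6.2.2. It does not settle the narrower direct-attribution phrase in the endpoint.

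Third, this is an abbreviated protocol with broken cross-references, so a mapping may exist in the full protocol or the eCRF. That is a real reason for caution about the missing mapping. It does not cure the definitions printed here.

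A reader might go further and infer the following, which the documents do not support:

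- *That SAEs rated Unlikely are excluded from the endpoint.* No section says so.
- *That the relatedness tables will mislead.* Section 6.2.2 does not say they use the tier names, so they may mislead only if they do.
- *That the top label is equally wrong.* The distance from *Probably/highly probably* to clearly caused is slight; the firm mismatches are two.

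**Conclusion.** The point holds. Two labels in 5.3.3 contradict their definitions, a remotely related event has no proper tier, and the pattern criteria hold a clearly device-caused but novel event at *Unlikely* or leave it unclassified. These are stated rules, not omissions. Because such ratings may feed a zero-event endpoint whose attribution phrase is tied to no tier or category in the supplied text, one SAE's rating could decide the primary safety result.

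That effect is conditional. It needs an SAE within 30 days, a rating in a disputed tier, and no mapping elsewhere. The 0/74 and 1/74 figures assume that all planned participants are treated.

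The missing mapping alone would be absent detail in an abbreviated document; it matters here because the tiers it would rest on are faulty. Confidence is high for the label mismatch and moderate for the missing mapping. The sponsor should correct this, but it does not by itself undermine the trial.

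**What to change.** In 5.3.3:

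- Reword the tiers so that labels and definitions agree, for example *possibly* for plausible and *probably* for more probable than not, and add a genuine *unlikely* tier for a remote chance.
- Change *and* to *or* in the list that asks for one criterion.
- State that the lack of a known pattern does not by itself lower a rating.

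In 6.2.1, state before analysis, and without loosening the endpoint, which corrected tier or tiers count and how attribution to the device is separated from attribution to the procedure. Reconcile this with 5.3.1 and 5.1.5, and apply the same rule to the related-event summaries in 6.2.2 and the device related proportions in 6.6.1.

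The cost is a wording amendment with IRB/HREC approval and, if required, FDA approval (8.7), and possibly one eCRF field. Events already rated would need re-mapping. Since some label words would change meaning, old and new label versions must be kept distinct in the data. More events may end up labelled related. No sample size or test changes.
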